**University of Rochester Medical Center**

## **1. STUDY OVERVIEW – PURPOSE AND BACKGROUND**

Alcohol use disorder (AUD) is a prevalent and consequential condition (Grant et al., 2015; Hasin & Grant, 2015). Unfortunately, even though obtaining alcohol-related care is associated with both improved drinking outcomes and recovery for those with AUD (Cunningham, 2005; Trim, Schuckit, & Smith, 2013), those with the disorder who end up getting help average going 18 – 20 years before doing so (Blanco et al., 2015). In fact, one of the strongest predictive factors for individuals to seek treatment is whether they have previously sought treatment (Blanco et al., 2015), making that first step all the more crucial to their lifetime prognosis. A recent treatment development study (R21 AA07143) adapted a novel and comparatively brief intervention based on Cognitive Behavioral Therapy delivered over the telephone, and found that it led to significantly increased use of alcohol-related treatment (Stecker, McGovern, & Herr, 2012).

The current study is a phase-II RCT using a two-group parallel design to further and more extensively test the efficacy of this intervention (CBT-TE) to promote use of alcohol-related care and improve drinking outcomes. Participants (n=450) will be recruited through advertisements, screened for eligibility by telephone, and those who are interested in participating and eligible will be consented, followed by administration of part one of a baseline assessment. Next, participants will be randomized to an intervention condition (45-60 minute CBT-TE intervention) or a control condition (being read a NIAAA brochure on AUD treatment). Participants are administered one of these interventions immediately following completion of part two of the baseline assessment which is to be completed within 21 days of part one of the baseline assessment. Follow-up assessments of alcohol-related treatment use and alcohol consumption will be conducted at 1,3, and 6 months after the administration of part one of the baseline assessment, with the assessors blinded to study condition. Prior to June 1, 2022, 9-month and 12-month follow-up assessments will also be conducted. On June 1, 2022 and after, follow-up assessments will be limited to 1, 3, and 6 month follow-ups.

## **2. CHARACTERISTICS OF THE RESEARCH POPULATION**

### **2.1. Subject Characteristics**

Participants will be adult residents of The Greater Rochester, Buffalo, and Syracuse Area with most likely being from Rochester and Buffalo specifically.

- a) **Number of Subjects:** Approximately 450 participants will be recruited into the study.
  - a. *What is the total (maximum) number of subjects to be enrolled (or their records/specimens accessed) at the University of Rochester (and other institutions if applicable to a multi-center study)? The total should include the number of evaluable subjects (i.e., those who meet eligibility criteria), as well as the number of anticipated screen failures necessary to obtain the enrollment goal. A subject is considered in the total count once informed consent has been obtained (as applicable). If evaluable subjects who withdraw from the study will be replaced to meet the enrollment goal, this should also be stated here.*
- b) **Gender and Age of Subjects:** Participants will be age 18 and older and based on prior experience of the study team (Stecker et al., 2012), we further expect that 56% of participants will be male, 44% will be female, and the mean age will be 40 years old.
- c) **Racial and Ethnic Origin:** Based on the demographics of Monroe County, it is expected that the racial composition will be approximately 65% white, 32% black, 3% Asian, and <1% American Indian/Alaskan Native. Ethnic composition is expected to be approximately 13%

Hispanic or Latino and 87% non-Hispanic.

## 2.2. Inclusion and Exclusion Criteria

- a) **Inclusion Criteria:** 1) age 18-plus; 2) score  $\geq 16$  on AUDIT; 3) within the past 30 days, exceeding the limits for low-risk drinking adopted by NIAAA:  $>3$  standard drinks on any occasion or  $>7$  drinks per week (women);  $>4$  drinks on any occasion or  $>14$  drinks per week (men).
- b) **Exclusion Criteria:** 1) unable to communicate with the researcher in English; 2) unable to comprehend the nature of the study; 3) history of alcohol-related care; 4) alcohol withdrawal necessitating medical evaluation; 5) residency outside of The Greater Rochester, Buffalo, and Syracuse Area; 6) Providing false information such as false name, contact information, or study responses.

## 3. SUBJECT IDENTIFICATION, RECRUITMENT, WITHDRAWAL AND CONSENT

### 3.1. Method of Subject Identification and Recruitment

Study participants for the proposed project will be recruited within the Greater Rochester, Buffalo and Syracuse Area. The Greater Rochester, Buffalo, and Syracuse area can be defined as the 17 surrounding counties: Orleans, Genesee, Wyoming, Monroe, Livingston, Ontario, Yates, Wayne, Seneca, Steuben, Niagara, Erie, Cortland, Madison, Oneida, Onondaga, and Oswego. Moreover, study participants for the proposed project will be recruited through a varied of online advertisements (e.g., Facebook, Instagram, Digital Banners, Craigslist, Reddit, Paid Search Ads, etc.) and local television, Print, and radio advertisements. Any use of digital advertisements will direct potential participants to a landing page where they can get in contact with the study team. IRB approved documents may also be used (e.g. flyers, billboards, digital signage, banners, etc.) in select targeted locations such as local bars, University affiliated healthcare clinics and hospitals, supermarkets, and other relevant locations. Advertisements will consist of an appropriately brief study description (based on the advertisement method) and contact information for interested persons to privately reach out for further information.

Recruitment for the study will also include the use of ResearchMatch, a national health volunteer registry that was created by several academic Institutions and supported by the U.S. National Institutes of Health as part of the Clinical Translational Science Award (CTSA) programs. ResearchMatch has a large population of volunteers who have consented to be contacted by researchers about health studies for which they may be eligible. Review and approval for this study and all procedures was obtained from the IRB.

Individuals inquiring about the study will be provided a brief overview and, if interested, screened using the 10-item AUDIT, 4-items from the National Survey of Drug Use and Health (NSDUH; Center for Behavioral Health Statistics and Quality, 2015) to determine if alcohol use within the past 30 days exceeds the limits for low-risk drinking adopted by NIAAA, and screening items on the Alcohol Use Disorders and Associated Disabilities Interview (AUDADIS; Grant et al., 2011) to determine if there is any history of professional alcohol-related treatment.

### 3.2. Circumstances for Withdrawal

Participants may be withdrawn from the study if they cannot keep appointments for study visits, if they cannot complete study activities, if study funding has been terminated, if alcohol withdrawal necessitating medical is required, or if subjects provide false information (false name, contact information, study responses etc.).

If a subject is withdrawn early, they will be notified of the following: No further information from them is required, they are being discontinued from the study, and that no further research session will be scheduled or take place. In addition, if the study subject is withdrawn before

treatment (a one-time phone intervention meeting), then treatment will not be provided. However, if it is discovered that the subject should be withdrawn after the treatment was provided, then the delivery of the treatment would not be affected but any subsequent follow-up assessments would be discontinued. Furthermore, no follow-up data will be continued to be collected and the information that they provided may not be used in study analysis and will be protected (see confidentiality of data and information storage). Lastly, these subjects will be replaced.

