Missing data: Missing data will be addressed in two ways. First, all models performed in a structural equation modeling framework will use a full information maximum likelihood (FIML) estimator robust to non-normality to account for missing data over time (108). These methods yield unbiased estimates and appropriate standard errors without sacrificing cases (thus maximizing statistical power) when data are missing completely at random or predicted by other variables in a given model but independent of the values of the outcome itself (i.e., missing at random). Statistical comparisons on baseline data (e.g., treatment condition, participant sex, alcohol-related severity) will be made between cases retained and those lost at follow-up to determine differential attrition and which covariates require inclusion in the models to meet the missing at random assumption. Mplus has a variety of FIML estimators for use with different outcome distributions and model specifications. Second, following much of the literature examining RCTs, we will apply intention-to-treat principles to data missing at follow-up (109). Specifically, we will ascribe undesirable values to all missing data points (e.g., assume no treatment use has occurred). Estimates from each method for handling missing data are valuable, as the FIML approach will provide a reasonable estimate of the true intervention effect whereas the intention-to-treat approach will provide lower bounds of the efficacy of the intervention.

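### Protocol 3.2 permits randomised participants to be dropped from follow-up and analysis and then replaced, and the SAP defines no analysis set that rules this out

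*Protocol*

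**What the plan says.** Protocol 3.2 says that participants may be withdrawn "if they cannot keep appointments for study visits, if they cannot complete study activities". The other grounds are loss of funding, alcohol withdrawal needing medical care, and false information. The section covers withdrawal before and after the session. For withdrawal after the session, "any subsequent follow-up assessments would be discontinued". It goes on: "Furthermore, no follow-up data will be continued to be collected and the information that they provided may not be used in study analysis". It ends: "Lastly, these subjects will be replaced".

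The SAP, under Missing data, gives two methods. The first is full information maximum likelihood (FIML), described as working "without sacrificing cases (thus maximizing statistical power") when data are missing completely at random or at random. The second is labelled intention-to-treat: "we will ascribe undesirable values to all missing data points (e.g., assume no treatment use has occurred"). The SAP does not mention withdrawn participants, removal of their data, or replacements, and it defines no analysis set. Protocol 8.1, where the analysis plan would stand, holds only the template question.

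On numbers, the SAP speaks of 450 at baseline, and Protocol 2.1 of about 450 recruited. The template text left in 2.1 asks for any replacement of withdrawn subjects to be stated there. It is not.

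**The concern.** Both documents place randomisation before the session. Protocol 1, read in order, puts it after part one of the baseline assessment, with part two and the session up to 21 days later. The SAP puts it after the baseline assessment. A rule that covers withdrawal after the session therefore reaches randomised people, and it can also reach some who are withdrawn before the session.

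Missing appointments and not completing activities are behaviours that can follow randomisation and may be related to whether someone seeks alcohol treatment, which is the Aim 1 outcome. If such people are removed and others take their place, the groups compared are no longer those that randomisation formed. Aim 1 is the comparison on which the study is powered. Two analysts following these documents in good faith could also analyse different sets of people.

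**Working it through.** **1. The texts side by side.** The words *may not* in Protocol 3.2 have two readings.
- As a prohibition: data from withdrawn people must be left out. The SAP's second method, read plainly, keeps them in and counts missing outcomes as no treatment use. The documents then conflict.
- As a possibility: data might or might not be used. There is no direct conflict, but who is analysed rests on a choice with no stated rule, timing or blinding.

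Protocol 2.1, 3.3, 8.1 and 8.2 and the SAP's Missing data text do not settle which reading applies.

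**2. The plan's own power figure.** Inputs from the SAP: 12% against 24%, 225 per arm, two-sided alpha 0.05. With a continuity-corrected two-proportion approximation:
- corrected difference: 0.12 − 1/225 = 0.1156
- null term: 1.96 × √(2 × 0.18 × 0.82 / 225) = 0.0710
- standard error: √((0.12 × 0.88 + 0.24 × 0.76) / 225) = 0.0358
- power: Φ((0.1156 − 0.0710) / 0.0358) = 0.894

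At 202 and 180 per arm the same formula gives 0.856 and 0.810. The SAP states 0.89, 0.86 and 0.81, so its figures reproduce. Without the correction the first is 0.915. The SAP's calculation treats loss as attrition out of 450 and does not mention replacement.

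**3. Bias if withdrawn people are excluded and replaced.** Assumptions, not taken from the documents: withdrawn share *w* in each arm and treatment use *u* among the withdrawn. True use is 12% in both arms (the SAP control rate), with 225 analysed per arm. The analysed rate in an arm is (0.12 − *w* × *u*) / (1 − *w*). For example, with *u* = 0, 0.12/0.90 = 13.33% and 0.12/0.98 = 12.24%, a relative risk (RR) of 1.09.

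Error is the chance of a two-sided significant result when there is no true effect. The uncorrected column uses the pooled z-test (normal approximation). The corrected column uses exact enumeration of the continuity-corrected test.

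| Withdrawn, CBT-TE vs control | *u* | Analysed rates | RR | Error, uncorrected | Error, corrected |
|---|---|---|---|---|---|
| equal, 10% vs 10% | 0% | 13.3% vs 13.3% | 1.00 | 5.0% | 3.5% |
| 3% vs 1% | 0% | 12.4% vs 12.1% | 1.02 | 5.1% | 3.5% |
| 10% vs 2% | 0% | 13.3% vs 12.2% | 1.09 | 6.4% | 4.6% |
| 10% vs 2% | 4% | 12.9% vs 12.2% | 1.06 | 5.6% | 4.0% |
| 20% vs 5% | 0% | 15.0% vs 12.6% | 1.19 | 11.2% | 8.6% |
| 20% vs 5% | 4% | 14.0% vs 12.4% | 1.13 | 7.8% | 5.8% |
| 2% vs 10% | 0% | 12.2% vs 13.3% | 0.92 | 6.4% | 4.6% |

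If the withdrawn use treatment at 12%, there is no bias. At 16%, withdrawal of 10% vs 2% gives 11.56% vs 11.92%, RR 0.97. The planned Mplus model is neither of these tests, so the error columns are a guide only.

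**4. Under the planned effect.** Take 24% vs 12%, with the withdrawn using treatment at one third of their arm's rate. At 10% vs 2%: (0.24 − 0.10 × 0.08)/0.90 = 25.8% and (0.12 − 0.02 × 0.04)/0.98 = 12.2%, so a true RR of 2.00 becomes 2.12. At 20% vs 5% the rates are 28.0% and 12.4%, RR 2.25.

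**5. Numbers randomised.** With equal allocation, as the SAP specifies, analysing 450 in total needs 450 / ((0.90 + 0.98)/2) ≈ 479 randomised at 10% vs 2%, and 450 / ((0.80 + 0.95)/2) ≈ 514 at 20% vs 5%. The analysed arms would then be about 215 and 235, or 206 and 244, and the error rates barely change.

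**6. Power.** With an assumed equal withdrawal of 20%, corrected power is 0.89 if the withdrawn are dropped and replaced, 0.81 if dropped and not replaced, 0.79 if kept as non-users without replacement, and 0.88 if kept as non-users with replacements added. Power is a lesser matter than bias here.

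**The case against.** The strongest reply is that the rule is narrower than it looks. The sentence on data use follows one about discovering, after the session, that someone should be withdrawn. That fits false information, which is also an exclusion criterion in 2.2, better than missed calls. The replacement sentence may share this target, and the numbers could then be small. This reading is fair, but the text does not limit either sentence to that ground.

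Blinding also counts. The SAP keeps the Rochester staff who do follow-ups unaware of assignment. If they decide on withdrawals, which the documents do not state, a staff-driven difference between arms is less likely. A difference driven by participants' behaviour remains possible. It is more plausible under the SAP, where the control session can be given at once and the CBT-TE appointment falls within a week. It is less plausible under the later protocol text, which gives both arms their session directly after part two of baseline.

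Other provisions help only in part. Protocol 3.3 says that the consent form covers retention and use of data. That form is not among the documents and may settle some of the retention question, but it would not be expected to define the analysis set. The template text in 2.1 counts a subject from consent, which bears on the total but is an instruction to the author, not a rule for analysis. The commitment to CONSORT in 8.2 does not say who is analysed.

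A reader might go further and infer three things that the documents do not support:
- That the SAP guarantees every case will be analysed. The phrase about not sacrificing cases describes a property of FIML under stated missing-data conditions.
- That one missed call leads to withdrawal. The payment terms in 4.2 and the SAP's attrition allowance assume that people can miss a follow-up and stay in the study.
- That the result will be biased towards CBT-TE. No withdrawal rate is given, and the bias can run either way.

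**Conclusion.** The point holds as a defect in the plan that should be fixed: Protocol 3.2 permits randomised people to be excluded and replaced, and nothing in the SAP prevents it. On one reading of 3.2 the two documents contradict each other. On the other, the analysis set is left open.

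Bias is possible, not shown. It requires that withdrawal differs between arms and is related to treatment use. In the illustrations, small or equal withdrawal matters little. At 10% vs 2%, the test that matches the SAP's power figures stays below 5%, although its error rises from about 3.5% to 4.6%. At 20% vs 5% with little or no use among the withdrawn, both tests exceed 5%. All these withdrawal rates and rates of use among the withdrawn are assumptions.

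The SAP also says that "the intention-to-treat approach will provide lower bounds of the efficacy of the intervention". Whether that is guaranteed is a separate, minor point about wording, because it can fail even when nobody is excluded: at withdrawal of 2% vs 10%, with 4% true use among the withdrawn counted as none, 11.92% vs 11.60% gives RR 1.03 when the truth is 1.00.

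**What to change.** Reconcile Protocol 3.2 with the SAP's Missing data text.
- State in the SAP that Aims 1 to 3 analyse all randomised participants in their assigned arm, keep data already collected, and handle later missing values by the two methods already planned.
- Limit exclusion to verified false information or ineligibility at baseline, judged blind to arm and outcome, with a sensitivity analysis that keeps these people where data exist.
- State in Protocol 2.1 and 3.2 that replacements add to, and do not substitute for, those randomised, and how they count towards 450.
- Report withdrawals and replacements by arm and reason.
- Where consent allows, keep attempting the 1-, 3- and 6-month assessments for people withdrawn only over appointments or incomplete activities. Amend the notice in 3.2, which now tells them that nothing further is needed. For the other grounds, state what data are kept and used.

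This concerns data retention and analysis only, not clinical handling. The cost is wording changes in the protocol, the SAP and possibly the consent form, plus a few more calls and $40 payments. The Aim 1 estimate may move in either direction compared with excluding these people.

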### 3.3. **Process of Consent**

Research staff will thoroughly go over the consent form with the participant by phone while clarifying any points as needed and answering all questions the subject may have. The informed consent will also be done with the aid of an interpreter for deaf/hard of hearing individuals as needed.

The informed consent form will contain a detailed description of the study procedures, along with statements regarding participants' rights to withdraw from the procedure at any time without consequences. It will be explained to participants in easy-to-understand language. The limits of confidentiality will also be explained, including the potential to break confidentiality in the acute risk of suicidal behavior or violence, or disclosures of unreported physical or sexual abuse of a child. This will occur prior to any data collection and the consent form will include text regarding the retention and use of that data.

Research staff will sign their name at the bottom of the form to show that they have explained the research, answered all questions to the subject's satisfaction, that the subject has demonstrated comprehension of the information, and provided oral consent to participate.

## 4. METHODS AND STUDY PROCEDURES

### 4.1. **Study Procedures and Assessments**

**4.1a. Assessments:** Nineteen relatively structured assessments will be used, which are described along with the schedule of administration in the table below. Each measure has been included in the online IRB application as appropriate. Supervision of the phone assessments for quality assurance (QA) will come in three forms:

1. The PI meets monthly with the IRB approved assessors to avoid drift in interviews, discuss any difficulties that arise, and answer any questions regarding the phone assessments.
2. The PI at the University of Rochester Medical Center or a Co-I at Syracuse University will act as a supervisor during select phone assessments. The purpose of this is to effectively complete a "check-in" to ensure that drift is not occurring and to provide feedback that might arise pertaining to assessment style and technique. The supervisor would be an IRB-approved Co-I or PI on the study team. The supervision of the phone assessment will occur by means of a three-way call, and when a supervisor does observes an assessment, the subject will be notified by the assessor at the start of the phone assessment (e.g. "my supervisor will be monitoring this phone call for quality assurance purposes"). At this point, the supervisor may also introduce himself/herself. Moreover, we will record in REDCap that instance for which live supervision was provided for a given follow-up assessment including the subject number, date of the follow-up assessment, the study assessor performing the assessment, and the investigator providing supervision (The co-I at Syracuse will not be receiving data, as his role pertains to provide QA). After the completion of the phone assessment (at this time the subject would have disconnected), the supervisor and the assessor would stay on the call and verbally go over the quality of the assessment (if time allows) or schedule a time to go over the feedback. The feedback to the assessor would address the following topics:

- a. Opening the interview:
- b. Establishing rapport:
- c. Neutrality:
- d. Listening:
- e. Reading items verbatim:
- f. Voice clarity:
- g. Information recorded accurately and completely:
- h. Probes used as needed:
- i. Closing the interview:
- j. Safety/human subjects' issues:

3. Lastly, [name] provides ongoing oversight of supervision through a weekly study conference call that he chairs and that includes all sub-investigators including sub-investigators from collaborating institutions.. During this call, the results of any supervisory observations will be discussed and any challenges that arose addressed. If there are instances that warrant further discussion, for example because an interview was problematic or an assessor requires further training, then [name] and the Co-I providing the supervision will schedule a time to talk 1:1 to make a plan for providing further training and supervision to the assessor. More specifically, [name] and [name], Co-I and Professor at Syracuse University, will be provide the supervision to the study assessors. Drs. [name] and [name] are on the weekly study conference calls as a matter of course, facilitating such coordination and oversight.

Measure	Screen	Baseline	Follow-Ups	Purpose
Preliminary Demographics	✓			Basic Information
NSDUH	✓		✓	Eligibility in Terms of AUG (Short-Term)
Lifetime Treatment Use	✓			Eligibility in Terms of Services
Substance-related sleep problems (SUSS)	✓		✓	Sleep QOL Assessment
AUDIT	✓			Eligibility in Terms of AUD (Long-Term)
Supplemental Demographics		✓		Describe Sample
TLFB		✓	✓	Substance Use

AUDADIS-V		✓		AUD Symptoms
ASSIST		✓	✓	Substance abuse in the past 30 days
DMQ-R		✓	✓	To assess the impacts of COVID-19 on drinking to cope with difficulties and emotion
INDUC		✓	✓	Substance Use
PHQ-2 and Standardized PHQ-4 Screener		✓	✓	Assess COVID-19 on sad mood & suicide risk screening triggered by PHQ-2
Treatment Use Update			✓	Utilization of AUD-Related Services
ATOS COVID-19		✓	✓	Assessing the impact of COVID-19 on a subject's lifestyle
Theory of planned Behavior (TPB)		✓	✓	Assessing the impact of COVID-19 related to telehealth
IMPASS*		✓	✓	Guides Therapy Session and Examine Change in Beliefs
WHOQOL – BREF		✓	✓	QOL Assessment
Insomnia Sleep Index		✓	✓	Sleep QOL Assessment
Debriefing Questions			✓	Understanding a Subject's experience

\*Administered immediately prior to delivery of the intervention condition or the control condition.

4.1b. Intervention Condition: Cognitive Behavioral Therapy for Treatment Engagement (CBT-TE) is a brief, tailored on-on-one session delivered by telephone lasting 45-60 minutes (Stecker, 2010). The intervention targets a change in the beliefs that influence whether or not someone initiates behavioral health treatment. During the session, participants are given a brief introduction to CBT and informed that it is based on the theory that cognitions, feelings, and behaviors all interact with each other. Therefore, since thoughts are modifiable, changing thoughts may lead to change in behavior. Based on a 3-step process, participants will be asked to

dispute beliefs about Alcohol Use Disorder (AUD) treatment elicited by the 39-item Identifying Modifiable Perceptions of Services Scale (IMPASS; Stecker, Fortney, Hamilton, & Azjen, 2007). A maximum of three beliefs will be discussed during the session and the participant and the interventionist will mutually agree upon beliefs to be discussed. All individuals assigned to the treatment condition will be administered the same structured intervention; however, content discussed within the session will differ for each participant based on their responses and thoughts surrounding the beliefs discussed within the session. Therefore, the intervention is structured but is not scripted.

**4.1c. Control Condition:** Control participants will be sent a NIAAA brochure on AUD treatment, either electronically or through regular mail. They will then be read the brochure over the phone by a study staff member, which is designed to offset effects that are attributable to attention. This brochure, titled “Treatment for Alcohol Problems: Finding and Getting Help” is included in the online IRB application.

